10.2 Baseline Values

Unless otherwise noted, baseline is defined as the last nonmissing value recorded prior to the first application of study drug. If time is not recorded and the assessment was on the same day as the first application of study drug, then it will be assumed the assessment occurred prior to the application of study drug. If a subject was randomized but not treated, then baseline is defined as the last nonmissing value on or before the date of randomization.

10.3 Adjustments for Covariates

The model for the primary efficacy will include adjustments for the following covariates: investigator type (dermatologist vs other), household number of randomized subjects (1 subject per household vs 2 subjects per household), age, and baseline lesion count. If there are not at least 3 responders and non-responders at each level of the stratification factors, then that stratification factor will be removed from the model. If there are fewer than 10 responders/non-responders, then neither investigator type nor household number of randomized subjects will be included in the model.

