Inflammatory reactions around the MC has been associated with imminent resolution of MC (sometimes referred to as “beginning-of-the-end” [“BOTE”] sign). The investigator (or designated evaluator) will assess the presence and overall degree of inflammatory reactions at MC lesions at Baseline (pre-dose) and Weeks 2-12. In most cases, clinical features can differentiate between BOTE and LSR. BOTE may be associated with itch, but not pain. BOTE is usually asymptomatic, self-limited, localized to individual MC lesions, and does not require discontinuation of study treatment or additional treatment. LSR is generally more diffuse, associated with significant itch or tenderness, may necessitate discontinuation of study treatment and may need treatment for symptomatic relief (e.g. a topical corticosteroid or topical anesthetic). For very severe LSR, systemic corticosteroids may be considered. Investigators will assess the treatment area at each scheduled visit and use their medical judgement to differentiate between BOTE and LSRs. BOTE Inflammation Score and LSR score will be recorded at each visit. BOTE should not be considered an AE. When LSRs are clinically significant at the application site, the Investigator should report the condition as AE(s).

At Baseline (30 min. post-dose) and Weeks 2 through Week 12 the evaluators will rate LSRs on individual features including erythema, flaking/scaling, crusting, swelling, vesiculation/pustulation, and erosion/ulceration using the BOTE Inflammation Score ([Section 7.2.3](#)).

Local Skin Reaction (LSR) Scores

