5.2 Inclusion Criteria

1. Be 6 months of age or older, and in good general health;
2. Have a written informed consent form signed by subject or a parent or legal guardian and an assent form as required;
3. Have between 3 and 70 treatable MC at Baseline;
4. Female subjects age 9 and above must have a negative UPT at Baseline;
5. Female subjects age 9 and above must agree to practice a medically acceptable form of birth control during the study and for 30 days after their final study visit;
6. Be willing and able to follow study instructions and likely to complete all study requirements.

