6.2.2 Visit 1/Baseline (Day 1)

The following procedures must be performed and recorded at the Baseline visit. If Screening and Baseline visits occur the same day, procedures with an asterisk (*) should only be performed once and will be recorded as Baseline values.

1. Complete age-matched Dermatology Life Quality Index (DLQI) assessment, as applicable.
2. Perform a brief physical examination.
3. Perform lesion mapping and lesion count.*
4. Perform BOTE Inflammation Score (pre-dose).
5. Obtain urine pregnancy test, as applicable. If pregnancy test is positive, the subject may not participate in the study.
6. Update concomitant medication information.

7. Confirm eligibility and randomize subject.
8. Dispense subject diary and study drug.
9. Weigh and record study product tubes.
10. Instruct subject on dispensing, mixing, and application of study product and diary completion.
11. Have subject/caregiver apply first dose in clinic from kit assigned at randomization.
12. Complete Local Skin Reaction assessment approximately 30 minutes post dose.
13. Collect and record AE information for any AEs reported.

6.2.3 *Visit 2/Day 2 Telephone Contact*

The following procedure must be performed and recorded at the Day 2 telephone contact.

1. Contact subject to confirm how the subject is feeling.

6.2.4 *Visit 3/Week 2 (Day 15 ±3)*

The following procedures must be performed and recorded at the Week 2 visit.

1. Perform lesion mapping and update lesion map with location for any new lesions.
2. Assess for subject recurrence of MC.
3. Review study compliance.
4. Dispense subject diary.
5. Review dosing instructions and have subject/caregiver apply daily dose in clinic using the kit assigned at randomization.
6. Perform BOTE Inflammation Score (post-dose).
7. Complete Local Skin Reaction Assessment (post-dose).
8. Collect and record AE information for AEs reported.
9. Update concomitant medication information and confirm if any new occurrences of MC were reported in the subject's household.

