5. DETERMINATION OF SAMPLE SIZE

Approximately 340 subjects, 6 months of age and older, with a minimum of 3 and a maximum of 70 MC lesions at Baseline will be randomized in a 2:1 (active:vehicle) scheme. The sample size assumptions for this study were informed by the completed Phase 2 study NI-MC201 of subjects 2 years of age and older with between 3 and 70 MC lesions at Baseline. In the Intent-to-Treat (ITT) Population of the Phase 2 study, the observed rates of complete clearance at Week 12 were 18% (12/66) for vehicle and 38% (18/48) for SB206 12% QD and the covariate-adjusted treatment difference was 18%.

A sample size of 340 subjects (227 subjects in the SB206 12% QD group and 113 subjects in the vehicle group) will provide 94% power for a 2-sided alpha test of size 0.05 to detect an absolute difference of 18% when the vehicle response rate is 18%. This same sample size provides 93% power to detect a treatment difference of 18% when the vehicle response rate is 20% and 83% power when the treatment difference is 15% and the vehicle response rate is 20%.

Since the intra-cluster correlation is estimated to be small (<10%) and the average size of households is expected to be capped at roughly 1.3, the sample size is still sufficient when considering the fact that the subjects within the household may not be independent.

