10.6 Examination of Subgroups

Subgroup analyses of complete clearance at Week 12 for investigator type (dermatologist vs other) and household number of randomized subjects (1 subject per household vs 2 subjects per household), and will be presented in a forest plot for the ITT Population. An additional subgroup analysis of complete clearance at Week 12 for age (<1 year old, ≥ 1 to <2 years old, ≥ 2 to <6 years old, ≥ 6 to <12 years old, ≥ 12 to <18 years old, ≥ 18 years old) and onset of MC symptoms duration prior to baseline (≤ 6 months vs >6 months) will be summarized descriptively for the ITT Population.

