12. OTHER ANALYSES

The following analyses of BOTE vs lesion count/complete clearance will be presented:

- Percent change from Baseline at Week 12 in relation to the highest BOTE score during treatment.
- Complete clearance at Week 12 in relation to the highest BOTE score during treatment.

- Percent change from Baseline at each visit in relation to BOTE score at Week 2.
- Complete clearance at each visit in relation to BOTE score at Week 2.

In these analyses, the BOTE scores will be analyzed in the ITT Population as follows:

1. Dichotomized:

- a. Score of 0 or 1: No to Mild
- b. Score of 2, 3, or 4: Moderate to Very Severe

A shift table comparing the baseline BOTE score to each scheduled postbaseline assessment will be presented for the Safety Population.

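### The pre-dose Baseline BOTE score, linked by the protocol to imminent resolution, enters no efficacy model, subgroup or baseline table, which forgoes some precision and leaves a chance imbalance uncorrected

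*Combined protocol and SAP*

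**What the plan says.** **Prognosis.** Protocol 4.1: "Inflammatory reactions around the MC has been associated with imminent resolution of MC".

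**Entry.** Protocol 5.2, criterion 3: "Have between 3 and 70 treatable MC at Baseline". None of the 13 exclusions in 5.3 concerns BOTE, so a subject whose lesions are already inflamed is eligible.

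**Collection.** Protocol 6.2.2, step 4: "Perform BOTE Inflammation Score (pre-dose". Randomization is step 7 of the same list.

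**Use in the final SAP** (the version whose output shells are numbered 3.0):
- 10.3 and 11.1: the model contains treatment, investigator type and "household number of randomized subjects (1 subject per household vs 2 subjects per household), age, and baseline lesion count". The Week 8 endpoint uses the same model (11.2).
- 10.6: "Subgroup analyses of complete clearance at Week 12 for investigator type (dermatologist vs other) and household number of randomized subjects" go into a forest plot. Age and symptom duration are summarized descriptively.
- 9.3: the baseline characteristics do not include BOTE.
- 12: clearance is related to BOTE through the peak on-treatment score ("Complete clearance at Week 12 in relation to the highest BOTE score during treatment") and through the Week 2 score. The Baseline score enters a Safety Population shift table.
- Appendix D: a by-visit BOTE summary (Table 14.2.3.10.5) and a listing (16.2.9.1), both Safety.

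**The concern.** The plan collects a baseline value that it describes as prognostic for the event it counts as success, and then leaves it out of every efficacy analysis. Two things follow. A model without a prognostic covariate is less precise than it could be. And if the arms differ by chance in the share of subjects already resolving at entry, no planned ITT analysis adjusts for it.

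The SAP 12 analyses do not fill this gap. The Week 2 score and the highest on-treatment score are both post-randomization. Under Table 1, footnote 4, BOTE is scored after dosing from Visit 3 onward, and its descriptors (erythema, edema, crusting, erosions) overlap those of the LSR scale. A drug reaction can therefore raise these scores, and an association with clearance cannot be separated from resolution already under way at entry. The Baseline score is the only one that treatment cannot have changed.

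**Working it through.** **1. Reproduce the plan's power.** Inputs (SAP 5): "227 subjects in the SB206 12% QD group and 113 subjects in the vehicle group"; the plan says this "will provide 94% power for a 2-sided alpha test of size 0.05" at 18% vs 36%. Normal approximation with pooled variance under the null:

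power = Φ[(d − 1.96·SE0)/SE1], where SE0 = √{p̄(1−p̄)(1/113 + 1/227)} and SE1 = √{pV(1−pV)/113 + pA(1−pA)/227}.

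For 18% vs 36%: p̄ = (113×0.18 + 227×0.36)/340 = 0.300, SE0 = 0.0528, SE1 = 0.0482, so (0.18 − 1.96×0.0528)/0.0482 ≈ 1.59 and power is 94.4%.

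| Vehicle / difference | Stated | Reproduced | With design effect 1 + 0.3×0.10 = 1.03 |
|---|---|---|---|
| 18% / 18 | 94% | 94.4% | 93.8% |
| 20% / 18 | 93% | 93.4% | 92.7% |
| 20% / 15 | 83% | 82.8% | 81.7% |

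The plan's figures reproduce. They rest on arm-level (marginal) rates, informed by the Phase 2 ITT results of 12/66 and 18/48.

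**2. Gain from adjustment.** The documents give neither the prevalence q of baseline BOTE nor the clearance rate b of BOTE-positive vehicle subjects. Both are assumed. The BOTE-negative vehicle rate is set to r = (pV − q·b)/(1 − q), which holds the marginal vehicle rate at the SAP value. A common odds ratio in both BOTE groups is chosen to give the SAP's marginal difference. Logistic regression without and with a binary BOTE term, 4,000 simulated trials per row, no household clustering and no other covariates:

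| q | b | 18% vs 36%: without → with | Gain | 20% vs 35%: without → with | Gain |
|---|---|---|---|---|---|
| 5% | 60% | 94.0 → 95.0% | 1.0 | 82.6 → 84.2% | 1.6 |
| 10% | 40% | 94.4 → 95.4% | 1.0 | 82.3 → 83.2% | 0.9 |
| 10% | 60% | 94.0 → 96.2% | 2.2 | 82.4 → 86.7% | 4.3 |
| 20% | 40% | 94.1 → 95.7% | 1.6 | 82.5 → 85.3% | 2.8 |
| 20% | 60% | 93.8 → 98.6% | 4.8 | 82.3 → 91.3% | 9.0 |

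The simulation error of a single power is about √(0.94×0.06/4000) = 0.4 points in the first scenario and √(0.83×0.17/4000) = 0.6 points in the second. Under another assumed prognostic strength over the same prevalence range, the gains were about 0.3 to 2 points and 1 to 3 points. The lower end is therefore close to nil in the first scenario.

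**3. Effect of an imbalance.** An excess e of BOTE-positive subjects in one arm moves that arm's rate by e × (BOTE-positive rate − BOTE-negative rate in that arm). Take e = 5 points, BOTE-positive clearance of 50-70%, and BOTE-negative clearance of 18% (vehicle) or 36% (SB206):
- Excess on vehicle: 0.05×(0.50 − 0.18) = 1.6 points, to 0.05×(0.70 − 0.18) = 2.6 points.
- Excess on SB206: 0.05×(0.50 − 0.36) = 0.7 points, to 0.05×(0.70 − 0.36) = 1.7 points.

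The range is 0.7 to 2.6 points.

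**4. How large an imbalance chance can produce.** The 95% limit is ±1.96·√{q(1−q)(1/113 + 1/227)}. With the marginal vehicle rate held at 18%, the resulting shift is that limit × (b − r):

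| q | 95% imbalance | Shift, b = 40% to 60% |
|---|---|---|
| 5% | ±4.9 points | ±1.1 to 2.2 points |
| 10% | ±6.8 points | ±1.7 to 3.2 points |
| 20% | ±9.0 points | ±2.5 to 4.7 points |

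**The case against.** **Dilution.** A reader might infer that admitting spontaneous resolvers shrinks the 18-point difference and undermines the power. With 10% or 20% BOTE-positive subjects who show no treatment effect, the difference would be 0.90×18 = 16.2 or 0.80×18 = 14.4 points. That follows only if 18% and 36% are the rates in BOTE-negative subjects. The vehicle rate would then run from 0.90×18% + 0.10×50% = 21.2% to 0.80×18% + 0.20×70% = 28.4%, which is not what SAP 5 assumes. The plan's rates are marginal and already include any spontaneous resolvers, so the documents do not support this reading.

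**Validity.** Randomization protects the type I error, and chance imbalance in an unmodelled covariate is already covered by alpha. This stands: the issue is precision and conditional imbalance, not bias.

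**Prognostic strength.** BOTE is localized to individual lesions but scored once per subject, and the endpoint requires a total count of zero in subjects who may enter with up to 70 lesions and acquire new ones. Inflammation at some lesions at entry may predict full clearance only weakly. This stands, and it is why the size is given as a range. Age and lesion count, already in the model, may absorb part of any effect.

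**Visibility.** The Baseline score is not wholly unused. SAP 6 presents summary tables by treatment group, so the shift table, and possibly the by-visit table, may show an imbalance. Because the first dose is applied in clinic at the randomization visit, the Safety Population should be close to ITT. What is missing is an analysis that corrects for it.

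**Timing.** Protocol 6.1 does not name BOTE among the procedures required before randomization, so only pre-dose scoring is guaranteed. Under blinding it is still a valid pre-treatment covariate.

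**Conclusion.** The point holds as an inexpensive improvement, not as a flaw in the primary test. A baseline value that the protocol itself calls prognostic is collected on the path to randomization and used in no efficacy model, subgroup or baseline-characteristics table.

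The benefit of adjustment is roughly 0-5 power points at 18% vs 36% and roughly 1-9 at 20% vs 35%. The upper ends need 20% prevalence together with 60% clearance in BOTE-positive vehicle subjects. If baseline BOTE is rare or weakly prognostic, the gain is negligible. The shift of 0.7 to 2.6 points from a 5-point imbalance is modest against the design difference of 18. All of these sizes rest on assumed prevalence and prognostic strength. The documents do not support a claim that the stated power is wrong or that eligibility biases the comparison.

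**What to change.** Before unblinding (SAP 6 makes anything later post hoc):

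- Prespecify baseline BOTE, 0-1 vs 2-4 (the cut already in SAP 12), as an added covariate in the Week 12 and Week 8 GEE models, at minimum as a sensitivity model. State which model is primary, because the odds ratio from the larger model is conditional on BOTE as well.
- Tabulate baseline BOTE by arm for ITT in 9.3. Showing all five score levels would keep mild inflammation visible, since the cut groups it with none.
- Add baseline BOTE to the 10.6 subgroups.
- Present the SAP 12 analyses of BOTE against lesion count and clearance by baseline BOTE level.
- Write a separate sparse-cell rule for this term. The removal rule in 10.3 covers only the stratification factors, and BOTE is not one.

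Leave the entry criteria unchanged. The cost is SAP wording and a few extra outputs. The score is already scheduled for every subject at Baseline, so no new data are needed.

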10.4 Handling of Dropouts or Missing Data

In analyses based on response, a missing response will be considered a nonresponder.

For a sensitivity analysis, subjects with missing lesion count at Week 12 but who demonstrated complete clearance at the last collected lesion assessment will be counted as responders.

10.5 Interim Analysis and Data Monitoring

When approximately 200 subjects (cumulative across studies NI-MC301 and NI-MC302) have completed 4 weeks of treatment, a DSMB will review all available unblinded safety data (including patch testing). All responsibilities of the DSMB and details of the analysis and data to be reviewed is detailed in the DSMB charter.

10.6 Examination of Subgroups

Subgroup analyses of complete clearance at Week 12 for investigator type (dermatologist vs other) and household number of randomized subjects (1 subject per household vs 2 subjects per household), and will be presented in a forest plot for the ITT Population. An additional subgroup analysis of complete clearance at Week 12 for age (<1 year old, ≥ 1 to <2 years old, ≥ 2 to <6 years old, ≥ 6 to <12 years old, ≥ 12 to <18 years old, ≥ 18 years old) and onset of MC symptoms duration prior to baseline (≤ 6 months vs >6 months) will be summarized descriptively for the ITT Population.

10.7 Multiple Comparison/Multiplicity

The familywise error rate with respect to the primary endpoint and secondary endpoint will be strongly controlled at the alpha=0.05 level using a fixed-sequence method testing strategy. If the primary endpoint is not statistically significant at the alpha=0.05 level, the secondary efficacy endpoint will be considered not significant. If the primary endpoint is statistically significant at the alpha=0.05 level, then the secondary efficacy endpoint will be analyzed. If the secondary efficacy endpoint fails to reach statistical significance at the alpha=0.05 level, it will be considered not statistically significant.

10.8 Multicenter Studies

This is a multicenter study, having approximately 35 centers participating in the study. The center effects will be investigated in the primary statistical analysis model by including the treatment by investigator type interaction. As exploratory analyses to examine the variability of the treatment effect across centers, the following analyses will be performed:

- Pool the centers into self-standing center pools of at least 17 subjects. The pooling will sort by investigator type and number of randomized subjects. Then, the centers with fewer than 17 subjects will be pooled until the self-standing center pool is at least 17 subjects. The treatment effect will be explored using a logistic model including treatment, household number of randomly assigned subjects, age, baseline lesion counts, and a strata statement which will include the pooling identified and examining the residual score statistics. To address treatment*center interaction, each pooling center will have a corresponding variable coded as 1 if on SB206 and 0 otherwise. Some pooled centers may have a p-value of less than 0.05 by chance since there will be multiple pooled centers.

- Pool the centers using the method above but the self-standing center pools will contain at least 10 subjects. This analysis should be interpreted with caution due to the small sample size within pooled centers.

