11. METHODS OF EFFICACY ANALYSIS

11.1 Primary Efficacy Analysis

The primary efficacy comparison will test the following hypotheses:

H_0 : The proportion of subjects with complete clearance is equal between SB206 12% QD and Vehicle;

H_1 : The proportion of subjects with complete clearance is different between SB206 12% QD and Vehicle.

The primary efficacy model will be the following for π_{H_i} as the probability of complete clearance for the i^{th} subject in household H:

$$\pi_{H_i} = \frac{e^{(\beta_0 + \beta_1 * X_{H_{i1}} + \beta_2 * X_{H_{i2}} + \beta_3 * X_{H_{i3}} + \beta_4 * X_{H_{i4}} + \beta_5 * X_{H_{i5}})}}{1 + e^{(\beta_0 + \beta_1 * X_{H_{i1}} + \beta_2 * X_{H_{i2}} + \beta_3 * X_{H_{i3}} + \beta_4 * X_{H_{i4}} + \beta_5 * X_{H_{i5}})}}$$

where H = Household, i = subject within the household, β_0 is the intercept,

$$X_{H_{i1}} = \begin{cases} 1, & \text{if treatment is SB206} \\ 0, & \text{if treatment is Vehicle} \end{cases}$$

$$X_{H_{i2}} = \begin{cases} 1, & \text{if subject is from a 2 subject household} \\ 0, & \text{if subject is from a 1 subject household} \end{cases}$$

$$X_{H_{i3}} = \begin{cases} 1, & \text{if subject is from a Dermatology site} \\ 0, & \text{if subject is from an Other site} \end{cases}$$

$X_{H_{i4}}$ is the subject's baseline lesion count, and $X_{H_{i5}}$ is the subject's age at baseline; treatment will be included in the class statement with PARAM=REF and REF=Vehicle. The working correlation will have an exchangeable structure. The model will include a repeated statement for subject household with household ID in the class statement. Also, the data structure will be ordered according to household ID and subject ID in household.

Treatment groups will be compared using a generalized estimating equation for logistic regression with an exchangeable working correlation structure. The model will include treatment, investigator type (dermatologist vs other), household number of randomly assigned subjects (1 subject per household vs 2 subjects per household), age, and baseline lesion count as factors. The odds ratio between SB206 12% and vehicle gel, 95% confidence intervals for the odds ratio, and P -value for the covariate-adjusted treatment comparison will be presented;

together with predicted proportions along with their associated 95% confidence interval. The difference in proportion confidence interval will be calculated using the following formula:

$$(p_{SB206} - p_{Vehicle}) \pm z_{0.025}^* * SE$$

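### SAP 10.8 includes the treatment-by-investigator-type interaction in the primary model, while SAP 10.3, SAP 11.1 and protocol 12.1.2 specify main effects only, and no contrast is named for the primary odds ratio if the interaction is in

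*Combined protocol and SAP*

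**What the plan says.** SAP 11.1 writes the primary GEE logistic model out in full. It has an intercept and five coefficients, for treatment, household number, investigator type, baseline lesion count and age. Investigator type is a 0/1 variable with 1 for dermatology sites and 0 for Other sites. For treatment, "treatment will be included in the class statement with PARAM=REF and REF=Vehicle". The prose repeats the terms: "The model will include treatment, investigator type (dermatologist vs other), household number of randomly assigned subjects", then age and baseline lesion count. There is no product term, and one odds ratio with its interval and p-value is to be presented.

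SAP 10.3 ("The model for the primary efficacy will include adjustments for the following covariates") lists the same four covariates, and protocol 12.1.2 has the same terms.

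SAP 10.8 differs: "The center effects will be investigated in the primary statistical analysis model by including the treatment by investigator type interaction". The sentence that follows applies the label exploratory to the two pooled-center analyses. It does not apply it to the interaction.

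**The concern.** A model with a treatment-by-investigator-type product has two treatment odds ratios, one per site type. SAP 11.1 asks for one, and nothing says how it would be formed. This matters for four reasons.

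- The primary p-value gates the Week 8 test in the fixed sequence of SAP 10.7.
- Week 8 and the responder-type exploratory endpoints are analyzed in the same way as the primary, so they inherit the question.
- The dropout sensitivity analysis combines a single log odds ratio for treatment across imputations, which presupposes that one exists.
- The sparse-data rules in 10.3 can remove investigator type but do not say what then happens to an interaction involving it.

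The rest of the SAP does not settle which model is meant. Appendix D lists tables for the pooled-center analyses (14.2.1.9 and 14.2.1.10) but none titled as a separate interaction model. Section 14 does not list the interaction as a change from the protocol.

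**Working it through.** **Inputs.** SAP section 5 gives "227 subjects in the SB206 12% QD group and 113 subjects in the vehicle group", which "will provide 94% power for a 2-sided alpha test of size 0.05" at 36% versus 18%. It also states 93% for 38% versus 20% and 83% for 35% versus 20%. The share *s* of subjects at Other sites is not in the documents; 30%, 50% and 70% are assumed.

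**1. Reproduce the stated power.** Pooled normal approximation: power = Φ[(d − 1.96·SE₀)/SE₁].

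- Pooled rate = (113×0.18 + 227×0.36)/340 = 0.300
- SE₀ = √[0.300×0.700×(1/113 + 1/227)] = 0.0528
- SE₁ = √[0.18×0.82/113 + 0.36×0.64/227] = 0.0482
- Power = Φ[(0.18 − 0.1034)/0.0482] = Φ(1.59) = 94.4%

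The other two cases give 93.4% and 82.8%. All three stated figures are reproduced.

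**2. What the treatment coefficient means with the interaction in.** Add β₆X₁X₃ to the 11.1 model. With X₃ = 0 for Other sites, the treatment log odds ratio is β₁ at Other sites and β₁ + β₆ at dermatology sites. So exp(β₁) and its p-value refer to Other sites only.

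**3. Power of that coefficient.** Only a fraction *s* of each arm contributes, so both standard errors grow by 1/√s and power = Φ[(d√s − 1.96·SE₀)/SE₁]. At s = 0.5 and 36% versus 18% this is Φ[(0.1273 − 0.1034)/0.0482] = Φ(0.495) = 69%.

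| Assumed Other share | 36% vs 18% | 35% vs 20% |
|---|---|---|
| 30% | 46% | 33% |
| 50% | 69% | 52% |
| 70% | 84% | 67% |
| Main effects, all subjects | 94% | 83% |

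A logistic simulation at 36% versus 18% (340 independent subjects, treatment and investigator type only, 2,000 runs per scenario) gave 45%, 70% and 84% for β₁, and 94% to 95% for the main-effects model.

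**4. Other contrasts from the interaction model.** The same simulation used a common effect and Other shares of 20% to 70%. Averaging the treatment effect over the observed site mix kept 94% to 95% power. Weighting the two site types equally gave 81% to 95%.

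**5. How far the readings can diverge.** Take 30% Other and an effect only at dermatology sites (36% versus 18%, and 18% in both arms elsewhere). The main-effects model gave a median odds ratio near 2.05 and rejected in 72% of runs. β₁ gave about 1.00 and rejected in 4%.

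**6. Type I error.** With no effect anywhere (30% Other, 4,000 runs), rejection was 4.7% for main effects and 3.7% for β₁.

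**7. The risk-difference interval in 11.1.** Its standard error takes the covariance of the two predicted log odds as (s²_SB206 + s²_Vehicle − s²_OR)/2. That is correct only if the log odds ratio is the difference between those same two predictions, which are made at the covariate means. Suppose half the subjects are at Other sites, rates are 36% versus 18%, and only treatment, site type and their product are in the model.

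- Variances of the predictions: SB206 1/(227×0.2304) = 0.0191; vehicle 1/(113×0.1476) = 0.0600; true covariance 0
- Variance of β₁: 2×(0.0191 + 0.0600) = 0.1582
- Covariance by the formula: (0.0191 + 0.0600 − 0.1582)/2 = −0.0395
- Correct SE²: 0.2304²×0.0191 + 0.1476²×0.0600 = 0.00232
- SE² by the formula: 0.00232 + 2×0.2304×0.1476×0.0395 = 0.00501

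The interval would be √(0.00501/0.00232) = 1.47 times its proper width.

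**The case against.** The strongest reply is that 11.1 governs. It is the section headed as the primary analysis, it writes the model out coefficient by coefficient, and 10.3 and the protocol agree with it. Section 10.8 speaks of investigating center effects, so fitting the interaction as an addition to the 11.1 model is a natural reading. Section 14 records no change to the primary model.

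The identity in step 7 also points away from an Other-sites odds ratio. It works if the model has main effects only, or if the odds ratio is the contrast at the covariate means. In neither case is the Other-sites effect the headline.

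Both arguments stand as evidence of likely intent. They do not remove the conflict: 10.8 says the term goes into the primary model, withholds the exploratory label from it, and names no contrast. Evaluation at the covariate means is stated for the predicted proportions but not for the odds ratio or p-value.

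Two further complaints would go too far. That investigator type is a poor stand-in for center is already met by the pooled-center analyses in 10.8. That the model could be chosen freely after unblinding ignores two safeguards: 11.1 pre-specifies a complete model, and SAP section 6 classes analyses performed after unblinding, beyond those in the plan, as post hoc.

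**Conclusion.** The final SAP contains conflicting rules for the primary model, and if the interaction is included the primary contrast is undefined. That much rests on the text alone.

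A reader might infer that the headline result will describe Other sites only, with far less power than stated. The documents do not support that as the expected outcome. It requires 10.8 to override the model in 11.1, and the raw treatment coefficient to be reported despite the standard-error formula. Under both conditions power for 36% versus 18% would be about 46% to 84% for Other shares of 30% to 70%, which are assumed. If 11.1 governs, or the contrast is averaged over the observed mix, it stays at about 94% when the effect is the same at both site types. Type I error of either single test is not inflated.

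The point still needs correcting before unblinding, because it concerns the test that gates Week 8 and the correction costs almost nothing.

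**What to change.** Replace the interaction sentence in SAP 10.8 with wording such as: *The treatment-by-investigator-type interaction will be examined in a separate supportive model that adds this term to the model in 11.1. The primary and Week 8 odds ratios, confidence intervals and p-values will come only from the main-effects GEE model in 11.1.* Add a line for the supportive model to Appendix D.

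This keeps the design's 94% power (94.4% by formula) and the validity of the risk-difference formula. It also makes the question about the 10.3 sparse-data rules irrelevant to the primary test. The cost is two sentences and one table entry before unblinding, with no change to data collection or sample size.
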